13.2 Efficacy Endpoints

Efficacy will be assessed by confirmed ORR, DOR, clinical benefit rate (CR + PR + SD ≥ 4 months), and PFS. Tumor response will be evaluated by the investigator using RECIST version 1.1. OS is not an endpoint of this study. Arms 1 and 2 will be analyzed completely separately.

13.3 Evaluable subjects

Patients who achieve sufficient compliance with the study drug intake in Cycle 1 (received at least 45 of 56 [greater than 80%] doses of mirdametinib (in Arm 1 only, also both doses of fulvestrant) **or** experience a DLT will be considered as evaluable for the assessment of the DLT rate for the particular dose level.

Additional patients should be enrolled at the same dose level as necessary to ensure an adequate number of DLT-evaluable patients.

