after the last dose of the last study drug (except for subjects who died, withdrew consent and objected to further data collection or were lost to follow up).

There will be no formal assessment of the overall survival in this study.

Arm 1 - Part 1 (Safety Run-in of Mirdametinib in Combination with Fulvestrant)

If permitted by the acceptable safety profile of mirdametinib 4 mg BID in combination with the standard recommended dose of fulvestrant, the Part 1 in Arm 1 of the study will be conducted as a single dose level. Patients with any MAPK pathway activating alteration as listed in section 6.1 will be included in this safety run-in, however patients harboring NF1 loss of function mutations will be prioritized, at the discretion of the principal investigator.

If mirdametinib 4 mg BID in combination with the standard recommended dose of fulvestrant is not tolerated well in the initial Dose Level, then a Dose Level de-escalation will be evaluated with mirdametinib 2 mg BID in combination with the standard recommended dose of fulvestrant. The Dose Level de-escalation will be evaluated according to the 3+3 design based on the incidence of dose-limiting toxicities (DLT) and the overall safety profile of the study treatments. The DLT definitions are listed in [Section 15.3](#).

At each step of the 3+3 design, the investigators will review all available safety and PK data at the current dose level and decide about the appropriate next step. The subjects will become evaluable for the 3+3 decisions if they complete Cycle 1 and receive at least 80% of doses at their assigned mirdametinib doses and all of their fulvestrant doses, or if they exhibit a DLT in Cycle 1.

Dose Selection: We note that the dosing of mirdametinib in the most recent phase II trial⁶ is 2 mg/m² twice daily, which translates to 4 mg twice daily in an adult population. However, the aforementioned study used an intermittent 3 weeks on / 1 week off schedule. This protocol is slightly different in that we are initiating a continuous dosing schedule of mirdametinib rather than intermittent. We believe that this schedule remains quite safe given that this dose is far below the MTD (15 mg BID) at which intermittent dosing was necessary to avoid toxicity.

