At each step of the 3+3 design, the investigators will review all available safety and PK data in the current Dose Level and decide about the appropriate next step. The subjects will become evaluable for the 3+3 decisions if they complete Cycle 1 and receive at least 80% of assigned drug doses, or if they exhibit a DLT in Cycle 1.

The starting dose of mirdametinib as single agent in each Dose Level escalation will be as follows:

- Dose Level 1: **mirdametinib 4 mg BID PO**, given continuously
- Dose Level 2: **mirdametinib 6 mg BID PO**, given continuously
- Dose Level 3: **mirdametinib 8 mg BID PO**, given continuously
- The de-escalation (Dose Level -1) may evaluate **mirdametinib 3 mg BID** given continuously, and (Dose Level -1INT) may evaluate **mirdametinib 3 mg BID** given on a 3 weeks on, 1 week off schedule. These de-escalation Dose Levels will be evaluated at investigator's discretion after the higher dose of mirdametinib is not tolerated. The de-escalation Dose Levels will be started only if the benefit-risk ratio is acceptable at the investigator's opinion.

The 3+3 decisions in Part 1 of Arm 2 will be made as follows.

1. Dose Level 1 (**mirdametinib 4 mg BID PO** given continuously)
 - a. Up to 3 subjects will be treated with mirdametinib as single agent at the dose of **4 mg BID PO** given continuously.

Memorial Sloan Kettering Cancer Center
[name]
[name]

- b. If 1 of the first 3 evaluable subjects in Dose Level 1 exhibit a DLT in Cycle 1, then Dose Level 1 will be expanded (see #2 below)
- c. If 0 of the first 3 evaluable subjects in Dose Level 1 exhibit a DLT in Cycle 1, then the dose of mirdametinib as single agent will be escalated to Dose Level 2 (**6 mg BID** given continuously) (see #4 below)

2. Dose Level 1 expansion:

- a. A sufficient number of subjects will be treated with mirdametinib as single agent at the dose of **4 mg BID PO** given continuously to accrue 6 evaluable subjects.
- b. If ≤ 1 of 6 evaluable subjects in the starting Dose Level exhibit a DLT in Cycle 1, then the dose of mirdametinib as single agent will be escalated to Dose Level 2 (**6 mg BID** given continuously) (see #5 below).
- c. If ≥ 2 of the first 3 evaluable subjects or ≥ 2 of the 6 evaluable subjects in Dose Level 1 exhibit a DLT in Cycle 1, then the mirdametinib dose will be de-escalated (see #3 below).

3. Dose Level -1 (de-escalation Dose Level **3 mg BID PO** given continuously)

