14.0 BIOSTATISTICS

14.1 Analysis Populations

The following analysis populations will be used:

- **DLT Evaluable Population** consists of patients who receive at least 80% of planned total doses of mirdametinib in cycle 1 (in Arm 1 only, also both doses of fulvestrant) and are observed within 28 days following the first dose of mirdametinib or patients who experience a DLT.
- **Efficacy Population**, used for the assessment of efficacy for each arm, will consist of all patients in Part 2 who received at least 1 dose of study drug and who have at least 1 post-baseline tumor assessment. Arms 1 and 2 will be analyzed separately. In addition, patients treated at the MTD in the dose escalation portion of the protocol (both arms 1 and 2) will be included in the efficacy analyses for the expansion cohorts in part 2 if they meet the requirements for efficacy population as defined above. Additionally, the RP2D will be determined pending the clinical data obtained in the dose escalation portion of the protocol. If the RP2D is less than the MTD, then patients treated at the RP2D in the dose escalation portion of the protocol (both arms 1 and 2) will be included in the

Memorial Sloan Kettering Cancer Center
[name]
[name]

efficacy analyses for the expansion cohorts in part 2 if they meet the requirements for efficacy population as defined above.

- **Pharmacokinetic Population**, used for the assessment of pharmacokinetic endpoints, will consist of all patients who have sufficient pharmacokinetic concentration data recorded to derive pharmacokinetic endpoints.
- **All treated population or safety population:** consisting of all patients who receive any amount of drug

Arms 1 and 2 will be analyzed separately throughout the study.

Arm 1

The study will follow a standard 3+3 dose escalation schema. As described previously in section 4.2, the 3+3 decisions in Part 1 of Arm 1 will be made starting with a mirdametinib starting dose level (4 mg BID PO), where subjects will be treated with mirdametinib 4 mg BID PO given continuously in combination with the recommended dose of fulvestrant. If ≤ 1 of the first 3 DLT evaluable subjects in Dose Level 1 exhibit a DLT in Cycle 1, then Dose Level 1 will be expanded. Mirdametinib dose in combination with fulvestrant will not be escalated above the 4 mg BID given continuously dose level.

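### Section 13.3 counts a DLT-free patient as evaluable without Cycle 1 completion or observation to Day 28, which conflicts with 4.2 and, when observation ends early, with 14.1

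*Combined protocol and SAP*

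**What the plan says.** The combined protocol and SAP defines DLT evaluability in several places.

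- **Section 13.3** requires "sufficient compliance with the study drug intake in Cycle 1 (received at least 45 of 56 [greater than 80%] doses of mirdametinib", and in Arm 1 both fulvestrant doses. Alternatively, patients who "experience a DLT will be considered as evaluable for the assessment of the DLT rate for the particular dose level". The section then gives the replacement instruction: "Additional patients should be enrolled at the same dose level as necessary to ensure an adequate number of DLT-evaluable patients".
- **Section 4.2, Arm 1 Part 1** sets the condition for entering the cohort decisions as follows: "if they complete Cycle 1 and receive at least 80% of doses at their assigned mirdametinib doses and all of their fulvestrant doses". A DLT in Cycle 1 also qualifies.
- **Section 4.2, Arm 2 Part 1** makes them "evaluable for the 3+3 decisions if they complete Cycle 1 and receive at least 80% of assigned drug doses", or with a DLT. The Arm 2 text of 14.1 repeats this rule.
- **Section 14.1, DLT Evaluable Population**, requires at least 80% of planned Cycle 1 mirdametinib doses (Arm 1: plus both fulvestrant doses) and that patients "are observed within 28 days following the first dose of mirdametinib or patients who experience a DLT".

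Section 15.3 sets the DLT window at Cycle 1, Day 1 to Day 28. Section 15.0 collects adverse events until 30 days after the last dose, or until another anticancer treatment starts if that is earlier.

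**The concern.** A patient without a DLT is informative for the full window only if the full window was observed. Section 4.2 and the DLT Evaluable Population each pair the dose threshold with a second condition, completion or observation. Section 13.3 keeps only the dose threshold, and it is also where staff would look to decide on replacement.

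The 3+3 decisions rest on 3 or 6 patients. If a patient leaves late in Cycle 1, a team reading 13.3 keeps that patient as DLT-free, while a team reading 4.2 enrols another. Counting an incompletely observed patient as DLT-free also pulls the estimated DLT rate down.

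**Working it through.** **1. The plan's threshold.** 28 days × 2 doses = 56. 0.80 × 56 = 44.8, which rounds up to 45. 45/56 = 80.4%, while 44/56 = 78.6%. The count in 13.3 is right for continuous dosing.

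**2. When the threshold is met.** 22 days × 2 = 44 doses, so with no missed doses the 45th is taken on Day 23. Fulvestrant in Cycle 1 is given on Days 1 and 15 (5.2), so the Arm 1 condition is already met. From the end of Day 23, 28 − 23 = 5 days remain, and 5/28 = 18% of the window.

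**3. Intermittent levels.** Dose Levels -2INT and -1INT plan 21 × 2 = 42 doses in Cycle 1. The 80% rule gives 0.80 × 42 = 33.6, that is 34 doses. A count of 45 cannot be reached.

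**4. The rules side by side, for a patient without a DLT.** The 14.1 clause is read here as observation through 28 days; its wording is loose.

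| Patient | 13.3 | 4.2 (and Arm 2 text of 14.1) | DLT Evaluable Population, 14.1 |
|---|---|---|---|
| 45 doses by Day 23; then withdraws, is lost or starts new anticancer therapy before Day 28 | Evaluable, not replaced | Not evaluable | Not evaluable |
| 45 doses by Day 23; stops drug, adverse-event follow-up continues past Day 28 | Evaluable | Not evaluable (Cycle 1 not completed, on its natural reading) | Evaluable |
| Intermittent level, all 42 doses taken, followed to Day 28 | Not evaluable | Evaluable | Evaluable |

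No row gives the same answer in all three columns.

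**5. Reproducing the plan's escalation table (14.1).** With the standard rule P(0 of 3) + P(1 of 3) × P(0 of next 3), true risks of 0.1 to 0.5 give 0.906, 0.709, 0.494, 0.309 and 0.172. These round to the stated 0.9, 0.7, 0.5, 0.3 and 0.2.

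**6. Effect of one truncated patient.** Assume a constant DLT hazard over 28 days and no observation after Day 23. At a true risk of 0.3, the observable risk for that patient is 1 − 0.7^(23/28) = 0.254. With one such patient among the first three:

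- P(0 of 3) = 0.7² × 0.746 = 0.366
- P(1 of 3) = 2 × 0.3 × 0.7 × 0.746 + 0.7² × 0.254 = 0.438
- Escalation probability = 0.366 + 0.438 × 0.343 = 0.516, against 0.494 with full observation

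At a true risk of 0.4 the change is from 0.309 to 0.331, and at 0.2 from 0.709 to 0.724. If every patient were truncated, an extreme bound, 0.494 would become 0.591.

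**7. The six-patient rule.** Arm 1 Dose Level 1 needs at most 1 DLT in 6. At a true risk of 0.3 this has probability 0.7⁶ + 6 × 0.3 × 0.7⁵ = 0.420. With one truncated patient it is (0.7⁵ + 5 × 0.3 × 0.7⁴) × 0.746 + 0.7⁵ × 0.254 = 0.437. The shift is of the same order.

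**The case against.** A reader might infer that 14.1 would exclude and replace anyone who stops mirdametinib on Day 23. The documents do not support that. The DLT Evaluable Population asks for observation, not Cycle 1 completion, and stopping drug does not end observation. Adverse events are collected for 30 days after the last dose unless other anticancer therapy starts. The end-of-treatment visit, 7 to 14 days after the last dose, would fall on about Day 30 to 37, after the window closes. Such a patient is normally kept by both 13.3 and 14.1; only 4.2 and the Arm 2 text of 14.1 exclude them. Progression alone does not end adverse-event follow-up either.

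A reader might also infer that dosing decisions are being taken under the laxer rule. The text that names the 3+3 decisions is the stricter one (4.2, repeated for Arm 2 in 14.1). Section 13.3 speaks of assessing the DLT rate.

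Both points stand and limit the size of the problem. They do not remove it. Section 13.3 carries the replacement instruction, and for a patient who leaves observation before Day 28 it gives the opposite answer to 4.2 and 14.1. In addition, the Schedule of Assessments has no Cycle 1 visit after Day 15. A patient lost after Day 23 may therefore have no scheduled haematology or chemistry beyond Day 15, although several DLTs in 15.3 are laboratory-based.

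**Conclusion.** The point holds as an internal conflict that should be fixed before cohort decisions depend on it. The conflict between 13.3 and 4.2 (with the Arm 2 text of 14.1) is firm. The conflict between 13.3 and the DLT Evaluable Population is conditional: it arises only when observation ends before Day 28. Section 4.2 and that population also disagree with each other on a patient who is off drug but still followed.

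The average statistical effect is small: about 0.02 on the escalation probability for one truncated patient among three at a true risk of 0.3. Even this assumes a constant hazard and no observation after Day 23, so it does not apply to a patient who remains under follow-up. The stronger reason to act is that one replacement decision in a cohort of 3 or 6 can go either way depending on the section.

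The fixed count adds a separate failure. Read literally, no DLT-free patient on a 3-weeks-on/1-week-off level could be evaluable under 13.3.

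**What to change.** Reconcile 4.2 (both arms), 13.3 and 14.1 (the population and the Arm 2 text) into one definition, worded identically. A patient is DLT-evaluable who either has a DLT in Cycle 1, or has received at least 80% of the mirdametinib doses planned in Cycle 1 for the assigned schedule (Arm 1: plus both fulvestrant doses) and has been observed through Day 28.

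Then add two statements:

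- A DLT-free patient whose observation ends before Day 28 is not evaluable and is replaced, whatever the number of doses taken.
- How a patient who stops drug early but is followed to Day 28 is classified, since 4.2 and 14.1 now differ on this.

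The 13.3 sentence should not be copied into the other sections as it stands, because that would carry the count of 45 to the intermittent levels. The percentage form avoids this.

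The cost is a short edit in three sections and occasionally one extra run-in or escalation patient, which 4.2 already implies.

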10.1 Mirdametinib Study Treatment

- Subjects will be instructed to take mirdametinib at home and record the time of intake for both daily doses in the patient dosing diary. Missed doses will also be recorded in the dosing diary. Subjects will be instructed to **not** take their planned morning dose of mirdametinib prior to each study visit during the treatment period. Instead, the morning dose will be taken following the pre-dose PK blood draw or any other assessment scheduled to be obtained at pre-dose during the visit.
- Mirdametinib treatment will be dispensed to subjects every two Cycles during scheduled study visits as described in the SoA or at an unscheduled visit if mirdametinib treatment is damaged/lost.
- Throughout the treatment period, subjects will self-administer study treatment BID utilizing a continuous dosing schedule in 28-day Cycles.
- Subjects will be instructed to swallow capsules whole and not to open or chew them prior to swallowing.
- No capsule should be ingested if it is broken, cracked, or otherwise not intact.
- Subjects should be encouraged to take their dose approximately every 12 hours
- Subjects can take mirdametinib capsules without regard to food intake.
- Delivery of mirdametinib via nasogastric tube or gastrostomy tube is not allowed.
- If a subject misses a scheduled dose of study treatment, and it is within 6 hours of the scheduled dose, the subject should immediately administer the missed dose and resume study treatment in accordance with the normal administration schedule. If more than 6 hours has elapsed since the time of scheduled administration, the subject will **not** be instructed to administer the missed dose and to resume study treatment as prescribed.
- Subjects should not take 2 doses together to “make-up” for a missed dose.
- If a subject vomits any time after taking a dose, then they must be instructed not to take another dose to “make up” for vomiting, but rather, to resume subsequent doses as prescribed.

Memorial Sloan Kettering Cancer Center
[name]
[name]

- If a subject inadvertently takes 1 extra dose, then the subject should not take the next scheduled dose of study treatment. Only one dose should be skipped in this context.

The dose levels for mirdametinib are summarized as follows:

Dose Level -2INT	2mg PO BID, 3 weeks on/1 week off
Dose Level -2	2mg PO BID given continuously
Dose Level -1INT	3mg PO BID, 3 weeks on/1 week off

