Dose Level -1	3mg PO BID given continuously
Dose Level 1	4mg PO BID given continuously
Dose Level 2	6mg PO BID given continuously
Dose Level 3	8mg PO BID given continuously

In arm 1, dose level 1 of mirdametinib will be used in the safety run-in with fulvestrant and this dose will be used as the RP2D, otherwise dose de-escalation will be carried out. In this arm if that dose is not tolerated, this will proceed to dose level -2 with fulvestrant. If dose level -2 is not tolerated, dose level -2INT will be initiated. Arm 2 will follow a dose escalation 3+3 standard design, in which dose level 1 is the initial dose of mirdametinib, with additional dose levels 2 and 3. Pending DLTs in dose levels 1-3, this arm will proceed to dose level -1 using mirdametinib as monotherapy. If dose level -1 is not tolerated, dose level -1INT will be initiated.

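### The DLT-evaluability count in Section 13.3 (45 of 56 doses) cannot be met at the two intermittent dose levels, which plan only 42 doses in Cycle 1

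*Combined protocol and SAP*

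**What the plan says.** Section 13.3 (Evaluable subjects) counts a patient towards the DLT rate of a dose level if the patient "received at least 45 of 56 [greater than 80%] doses of mirdametinib", plus both fulvestrant doses in Arm 1, or if the patient has a DLT. The rule applies to each dose level and does not mention schedule. The section adds that further patients should be enrolled at the level until enough are evaluable.

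The same definition appears elsewhere as a proportion:

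- Section 4.2, Arm 1 Part 1: patients must "complete Cycle 1 and receive at least 80% of doses at their assigned mirdametinib doses and all of their fulvestrant doses", or have a DLT.
- Section 4.2, Arm 2 Part 1: patients are evaluable "if they complete Cycle 1 and receive at least 80% of assigned drug doses", or with a DLT. Section 14.1 repeats this for Arm 2.
- Section 14.1, DLT Evaluable Population: "patients who receive at least 80% of planned total doses of mirdametinib in cycle 1" and who are observed over the 28 days, or who have a DLT.

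The dose-level table in Section 10.1 contains two intermittent levels: -2INT, "2mg PO BID, 3 weeks on/1 week off", and -1INT, "3mg PO BID, 3 weeks on/1 week off". Each is the last de-escalation step of its arm: "If dose level -2 is not tolerated, dose level -2INT will be initiated" for Arm 1 and "If dose level -1 is not tolerated, dose level -1INT will be initiated" for Arm 2. If an intermittent level also fails, the arm is discontinued (Section 14.1 for Arm 1, Section 4.2 for Arm 2).

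**The concern.** A fixed count of 45 doses was set for a 56-dose cycle and not adapted to the intermittent levels. A patient at -2INT or -1INT who takes every prescribed dose and has no DLT falls short of it. The only other way to be evaluable under 13.3 is to have a DLT.

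This bears on a stop/go decision. What decides the step is the number of DLTs among evaluable patients, so the rule for who is evaluable feeds directly into it. A literal reader of 13.3 would set aside and replace every DLT-free patient and keep only those with DLTs. Section 13.3 carries the title on evaluability and is the only place that prints a dose count, so it is a natural source for a data-management check.

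**Working it through.** **Inputs.** Cycle of 28 days (Section 4.2); twice-daily dosing (Section 10.0); 3 weeks on, 1 week off at -2INT and -1INT (Sections 4.2 and 10.1); threshold of 45 of 56 (Section 13.3); 80% of assigned or planned doses (Sections 4.2 and 14.1); acceptance if at most 1 of 6 evaluable patients has a DLT (Section 4.2).

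**Step 1: reproduce the plan's figure.** Continuous schedule: 28 × 2 = 56 doses. 0.80 × 56 = 44.8, so at least 45 doses (45/56 = 80.4%; 44/56 = 78.6%). The 45 of 56 is therefore the 80% rule for continuous dosing.

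**Step 2: apply it to the intermittent schedule.** 21 × 2 = 42 doses planned. 42 − 45 = −3, so full compliance is 3 doses short. On the 13.3 scale it is 42/56 = 75.0%, and the threshold is 45/42 = 107% of the planned doses.

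**Step 3: apply the 80% rule to the intermittent schedule.** 0.80 × 42 = 33.6, so at least 34 doses (34/42 = 81.0%; 33/42 = 78.6%). Whether the rule says at least 80% or more than 80% makes no difference, since neither 44.8 nor 33.6 is a whole number.

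**Step 4: consequence for the 3+3 rule.** Under the literal count every evaluable patient at an intermittent level has a DLT, so the observed DLT rate is 100% by construction. At most 1 of 6 is then unreachable. The only possible outcomes are discontinuation or never filling the cohort.

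**Step 5: how often an intermittent level is reached.** Assume that the true DLT risk p is the same at the two preceding levels and that patients are independent; write q = 1 − p. The probability that a level fails is

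- A = 1 − (q⁶ + 6pq⁵), if 0 or 1 DLT in the first 3 leads to expansion to 6;
- B = 1 − (q³ + 3pq² × q³), if 0 of 3 passes and only 1 of 3 leads to expansion.

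Example at p = 0.20: A = 1 − (0.2621 + 0.3932) = 0.3446; B = 1 − (0.5120 + 0.1966) = 0.2914.

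Arm 1: Dose Level 1 follows A. At Dose Level -2, Section 4.2 states expansion only for 1 of 3, so 0 of 3 may be read as a pass (B) or as expansion to 6 (A). The chance of reaching -2INT therefore lies between A × B and A × A.

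Arm 2: Dose Level 1 follows B in Section 4.2, and Dose Level -1 follows A, which gives B × A. Section 14.1 also says that Dose Level 1 is expanded at 0 or 1 of 3; on that reading the value for -1INT is A × A.

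| True DLT risk p | A | B | A × B | A × A |
|---|---|---|---|---|
| 0.05 | 0.0328 | 0.0266 | 0.09% | 0.11% |
| 0.10 | 0.1143 | 0.0939 | 1.1% | 1.3% |
| 0.20 | 0.3446 | 0.2914 | 10.0% | 11.9% |
| 0.30 | 0.5798 | 0.5057 | 29% | 34% |
| 0.40 | 0.7667 | 0.6907 | 53% | 59% |
| 0.50 | 0.8906 | 0.8281 | 74% | 79% |

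The rows from 0.10 to 0.50 are the risks in the plan's own escalation table in Section 14.1.

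**The case against.** The strongest reply is that the plan already contains a workable rule. Section 14.1 formally defines the DLT Evaluable Population as 80% of planned doses, and the 3+3 text in Section 4.2 uses 80% of assigned doses. Section 13.3 prints the percentage beside the count, so 45 of 56 can be read as an illustration for continuous dosing. A sensible team would not apply a threshold above the number of doses prescribed. On this view it is a drafting omission on a path that may never be taken.

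Much of this stands. The likely harm is two conflicting definitions at the decision, not a certain wrong stop, and nothing changes at the continuous levels as far as the dose count is concerned. But 13.3 states a decision threshold without qualification, and following it gives a wrong result. Good sense at the time is a weak safeguard when the choice between definitions would be made with the DLT data already known.

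It is also fair to say that the omission is not confined to 13.3. Section 10.1 describes dosing throughout as continuous, and footnote 5 of the Schedule of Assessments describes dosing on every day of the cycle. These do not rescue the count, because the dose-level table in Section 10.1 lists both intermittent levels.

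**Conclusion.** The concern holds. The 13.3 count is wrong as written for two of the seven dose levels in the Section 10.1 table: one of three in Arm 1 and one of five in Arm 2. The threshold there is 45 under 13.3 against 34 under 4.2 and 14.1, with 42 doses planned. This finding is arithmetic and needs no assumption beyond the stated schedules.

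How often it matters does rest on assumptions. With equal and independent DLT risk at the two preceding levels, an intermittent level is reached with a probability of about 0.1% at a risk of 5%, about 1% at 10%, 10–12% at 20% and 29–34% at 30%, and more often than not at 40% or above. These are upper values if the risk falls at the lower dose. In Arm 2 they are further limited because Section 4.2 leaves the de-escalation levels to the investigator's discretion. The point should be fixed, but it does not undermine the design.

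**What to change.** In Section 13.3, replace the fixed count by the plan's own proportional rule, for example: at least 80% of the mirdametinib doses planned for the assigned level and schedule in Cycle 1 (45 of 56 if continuous; 34 of 42 if 3 weeks on, 1 week off). Keep the fulvestrant condition for Arm 1 and the DLT route to evaluability.

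In the same edit, carry over the follow-up condition that 13.3 lacks. Section 4.2 asks for completion of Cycle 1 and Section 14.1 for observation over 28 days, while 45 twice-daily doses can be taken by Day 23 (45/2 = 22.5). One wording should be used in all three sections; the simplest way is to define the population once in 14.1 and refer to it elsewhere. The general dosing statement in Section 10.1 and footnote 5 of the Schedule of Assessments should also be reconciled with the dose-level table.

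The cost is one sentence in 13.3 plus the cross-checks. Sample size, dose levels, the DLT definition and the 3+3 decisions do not change.
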